6.12.2 Hospitalization due to worsening PAH

Any hospitalization due to worsening PAH that occurs from randomization to the 30 days following subject's last study visit is counted as an event for the primary outcome. The date of the event is the actual date of hospitalization. All those without a reported hospitalization during the 30 days following their last visit are censored for hospitalization at the 30 day time even if it is known that they were hospitalized after the 30 day window.

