Following the Baseline Visit, subjects will return to the study site for scheduled study visits at Week 4, Week 8, and Week 12 (first Quarterly Visit) and for scheduled Quarterly Visits thereafter. Subjects will undergo all scheduled efficacy and safety assessments as defined by the protocol and the Schedule of Events (Appendix 1). Between scheduled study visits, the subject will be contacted to assess for possible clinical worsening events and to record any newly occurring or changes to adverse events or concomitant medications. Subject contact should occur weekly for the first twelve weeks (except for study visit weeks) when subjects are becoming familiar with the study drug dosing (including up-titration to the fixed dose, as tolerated) and study procedures. Subjects should be contacted monthly between scheduled Quarterly Visits through the end of study participation.

Subjects will continue the study until it is formally concluded by the Sponsor. Following study conclusion the subject will return to the clinical site for an End of Study Visit to undergo all scheduled assessments. Subjects who are participating in the study at its conclusion may be offered the opportunity to enroll in a long-term open-label extension study.

In the event that a subject withdraws consent for participation in the study or the Investigator terminates the subject from the study the subject will be weaned from study drug and will return to the clinical site for an End of Study (Early Termination) Visit to undergo all scheduled assessments.

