Using the aforementioned published literature, the sponsor anticipates the one-year rate of clinical worsening will be approximately 15% for the population treated with inhaled treprostinil. As such, the sponsor considers the sample size necessary to show a clinically meaningful difference between the esuberaprost and the placebo groups treated with inhaled treprostinil to be prohibitively large. The sponsor intends to restrict recruitment to inhaled treprostinil subjects where an esuberaprost treatment effect will be more readily discerned. Following guidance from the Food and Drug Administration in 2012 (UCM332181) on clinical study enrichment strategies, the inclusion criteria of the current study (protocol, Section 5.2) specified that patients will be randomized into this study only if they are showing signs of deterioration after initial improvement on inhaled treprostinil treatment or have had a clinically suboptimal response to inhaled treprostinil treatment. The specific exclusion of subjects who are likely to be at a lower risk of clinical worsening will reduce the proportion of subjects available for recruitment; however, the targeted study population of those who have shown suboptimal response will be expected to have a higher event rate than would a broader population. Therefore, fewer subjects will be needed to test the hypothesized absolute effect size. Moreover, the target study population is one most likely to benefit from an additional therapy; without additional treatment, approximately 45% of these patients are expected to experience clinical worsening in a year.

Initial start-up activities and recruitment are restricted to ensure the safety of subjects. Therefore, the sample size calculations do not include the initial 6 months of the study to make certain the study has adequate power. The sample size calculations were based on the following assumptions:

- a one-year clinical worsening rate of:
 - 45% in the placebo group (inhaled treprostinil alone)
 - 25% in the esuberaprost group
- proportional hazards over time
- an accrual period of 1.5 years
- total follow-up time of 2.5 years (follow-up time for last subject randomized 1 year; total study duration 2.5 years)
- 0.01 two-sided significance level

[figure not shown]

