This study will randomize approximately 240 subjects (120 subjects per treatment group). Calculation of the sample size was based on the assumptions listed above. Under those assumptions, an exponential maximum likelihood test of equality of survival curves would require 113 events overall to detect a treatment difference at a power of 90% at a 0.01 two-sided significance level. Given the expected accrual period and follow-up time, an appropriate sample size is 240 subjects. There was no restriction or quota with respect to number of subjects by country.

Study sample size is based on a 0.01 two-sided significance level to provide sufficient power to observe ‘substantial evidence’ of effectiveness within a single clinical study. However, at the time of the analysis, the effect will be tested at a significance level of 0.05 (see Section 6.10). The power at a 0.05 two-sided significance level is 97%.

Sample size calculations were performed with nQuery Advisor 7.0 (2014) and PASS (Hintze, 2013) using sample size methods for the log-rank statistic based on Lakatos & Lan (1992).

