6.4.2 Handling of Missing Data

The sponsor acknowledges the implications of missing data on the integrity of study outcomes and, consistent with Fleming's recommendations (2011), implemented the following strategies to minimize the extent of missing data:

1. All subjects were allowed to continue in the study until the close of study, whether on IMP or not. Subjects were not to be summarily discontinued from the study, unless 1) the subject withdrew informed consent; 2) the subject met a primary endpoint and declined continuation in the study; or 3) the subject continued to be non-adherent to study protocol after repeated attempts to correct (at least 6 months). However, the subject has the right to discontinue from the study at any time. All subjects who discontinue the study, unless they withdraw informed consent, will continue to be followed, to the extent possible, for vital status until the sponsor concludes the study.
2. Recent publications (Sitbon et al., 2015; Galiè et al., 2015) have shown that roughly 20% of subjects prematurely terminate from mortality and morbidity studies in PAH. The sponsor has throughout the study engaged with study investigators to encourage subjects' retention in the study, adherence with the protocol, and compliance with IMP.
3. While the study protocol is necessarily complex in order to obtain the scientific data to evaluate the safety and efficacy of the IMP, the sponsor designed the protocol in the manner that was not burdensome to the subjects: 1) Much of the data collected for secondary endpoints is derived from assessments performed for 'standard of care' visits; 2) Study visits are minimal (quarterly) with permissive visit windows (\pm 10 days); 3) Use of optional substudies for exploratory endpoints; and 4) Sponsor-provided Tyvaso to all subjects in the study.

Methods for handling missing data will be described in the sections discussing each outcome.

No imputation is planned for missing safety or exploratory data.

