6.12 Primary Efficacy Analysis

As described in Section 2.1, the primary efficacy outcome is the TtCW, measured in days, where clinical worsening is defined as the first occurrence of any of the following:

- Death (all causes)
- Hospitalization due to worsening PAH
- Initiation of a parenteral (infusion or sub-cutaneous) prostacyclin directly related to worsening PAH
- Disease progression

- Unsatisfactory long-term clinical response

As described above, a blinded Event Adjudication Committee (EAC) will review all suspected clinical worsening events and make a final determination for each (see [Appendix 1](#)). The EAC Charter, Version [REDACTED], specifies evidence to be provided to the EAC along with the general rules and criteria for EAC confirmation of a primary endpoint of clinical worsening. Because the EAC Charter cannot address every possible scenario, the EAC Charter shall be viewed as a framework under which the EAC will operate. Each case will be determined on the basis of a consensus of the EAC, the members of whom are independent experts in PAH. Please see [Appendix 2](#) for general rules and criteria excerpted from the EAC Charter.

Subjects were not required to discontinue from the study after meeting a primary endpoint; thus, more than one clinical worsening event may be reported for the same subject. This section defines the calculation of time to each component of the primary outcome. The protocol specifies that investigators follow each subject for 30 days after the subject discontinues from the study to assess the occurrence of SAEs and for 90 days after the subject stops study medication for vital status. Further, the investigators are instructed to provide all clinical worsening events that occur after the primary clinical worsening event, as well as the vital status of all subjects at the time the sponsor terminates the study.

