6.12.1 Death (All Cause)

Deaths that occur at any time from randomization to 90 days after the subject's last study visit is counted as a death for the primary efficacy analysis. All those still alive 90 days after their last visit are censored for death at the 90 day time even if it is known that they died after the 90 day window.

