6.12.3 Initiation of a Parenteral (infusion or sub-cutaneous) Prostacyclin

Any initiation of a parenteral prostacyclin, directly related to worsening PAH (transient use [≤ 7 days] for non-PAH related illness allowable, that occurs from randomization to the 30 days following subject's last study visit is counted as an event for the primary outcome. The date of the event is the actual date of transition to parenteral prostacyclin. All those without a reported parenteral prostacyclin during the 30 days following their last visit are censored for parenteral prostacyclin at the 30 day time even if it is known that they received parenteral prostacyclin after the 30 day window.

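### SAP 6.12.1 to 6.12.3 run the primary-event windows from an undefined last study visit, so a confirmed on-study event can be dropped when the subject attends no later visit

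*SAP*

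**What the plan says.** SAP 6.12.1 to 6.12.3 set a counting window for three components of clinical worsening, each measured from the subject's last study visit.

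- **Hospitalization for worsening PAH (6.12.2):** counted to 30 days. Subjects with none reported by then are "censored for hospitalization at the 30 day time even if it is known that they were hospitalized after the 30 day window".
- **Parenteral prostacyclin (6.12.3):** counted to 30 days. Subjects with no start by then are "censored for parenteral prostacyclin at the 30 day time even if it is known that they received parenteral prostacyclin after the 30 day window".
- **Death (6.12.1):** counted to 90 days, with any later death ignored: "All those still alive 90 days after their last visit are censored for death at the 90 day time even if it is known".

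Neither document defines the last study visit. Other sections use different anchors:

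- SAP 6.12 says investigators "follow each subject for 30 days after the subject discontinues from the study to assess the occurrence of SAEs", and gives 90 days after stopping study medication for vital status.
- Protocol 10.1 censors only subjects who had no independently confirmed event during the study.
- Protocol 10.3 cuts efficacy evaluations at the last study visit or 30 days after permanent discontinuation of study drug.
- SAP 6.12.6 censors event-free subjects at the last study visit itself, with no added 30 or 90 days.

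On timing, Protocol 4.1 schedules visits at Weeks 4, 8 and 12 "and for scheduled Quarterly Visits thereafter". Quarterly visits have a window of ±10 days (Protocol 8.6, SAP 6.4.2). Between them, monthly calls assess clinical worsening (Protocol 8.2.2).

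**The concern.** A 30-day window does not span a quarterly interval. Take a subject seen at Week 24 who is hospitalized for worsening PAH at Week 32, 56 days later, and never attends again. The subject was on study. The site would learn of the event from the family, the hospital or the monthly call, and the EAC could confirm it. Under 6.12.2 it does not count. SAP 6.12.6 then either censors the subject as event-free at Week 24 or, if death follows by day 90, dates the event to the death.

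Not returning can be a consequence of the event itself. SAP 6.4.2 lists among the reasons for leaving the study that "the subject met a primary endpoint and declined continuation in the study", and Protocol 8.7 asks for an End of Study Visit only if possible. The subjects at risk of being cut off are therefore those whose event stopped them attending, so the censoring may be informative. The trial also stops at 113 events (Protocol 4.3, SAP 3.1), and the analysis could hold fewer than the number that triggered the stop.

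**Working it through.** **1. Reproduce the plan's own figures.** Inputs from SAP 4.1: one-year rates of 45% and 25%, 1:1 allocation, 113 events, a "0.01 two-sided significance level" for design, and the statement that "at the time of the analysis, the effect will be tested at a significance level of 0.05".

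- HR = ln(0.75)/ln(0.55) = 0.481, so |ln HR| = 0.731.
- Schoenfeld events for 90% power at 0.01: 4(2.576 + 1.282)²/0.731², which rounds up to 112, against 113 stated.
- Power with D events = Φ(√D/2 × 0.731 − z). At D = 113 this is 90.5% at 0.01 and 97.3% at 0.05, matching the stated 90% and 97%.

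**2. Share of a visit interval outside the windows.** For hospitalization and parenteral starts the share is (gap − 30)/gap.

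- 84-day gap: 54/84 = 64%.
- 91-day gap: 61/91 = 67%.
- Before Week 12 the nominal gaps are 28 days, so nothing is uncovered.

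For deaths the 90-day window covers an 84-day gap in full and falls short by 1 day at 91 days. Using both ±10-day windows, the gap can reach 84 + 20 = 104 or 91 + 20 = 111 days, leaving 14 or 21 days uncovered. After one missed visit at 84-day spacing, (168 − 90)/168 = 46% of the time is uncovered, but the death is lost only because no visit follows it.

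**3. Share of first events at risk.** Exponential first events were simulated at the planned hazards, with follow-up uniform over 1 to 2.5 years and nominal visit days. About 50% of first events (84-day spacing) or 52% (91-day) fall more than 30 days after the preceding visit. This is below 64% because of the closer early visits.

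**4. Events lost.** Lost = 113 × s × u × q, where:

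- s = share of first events that are hospitalization or parenteral start (not in the documents; range 0.4 to 0.8);
- u = 0.502, from step 3;
- q = share of the affected subjects who attend no later visit (not in the documents).

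Examples: 113 × 0.4 × 0.502 × 0.10 = 2.3, and 113 × 0.8 × 0.502 × 0.30 = 13.6.

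| q | Events lost (s = 0.4 to 0.8) | Power at 0.05 | Power at 0.01 |
|---|---|---|---|
| 5% | 1.1 to 2.3 | 97.2 to 97.1% | 90.2 to 89.8% |
| 10% | 2.3 to 4.5 | 97.1 to 96.8% | 89.8 to 89.1% |
| 20% | 4.5 to 9.1 | 96.8 to 96.2% | 89.1 to 87.5% |
| 30% | 6.8 to 13.6 | 96.5 to 95.4% | 88.4 to 85.8% |

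At 91-day spacing the worst of these cells becomes 14.2 lost, with power 95.3% at 0.05. The formula treats every affected event as lost. Some would return, later in time, as deaths inside the 90-day window.

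**5. Balance between arms.** With 120 per arm and the planned accrual and follow-up, the event probabilities are 0.637 and 0.391, giving about 76 and 47 events, a ratio of 1.6. A trial simulation assumed s = 60% and that 30% of non-returners die within 60 days. It lost 1.9 placebo and 1.2 active events at q = 10%, and 5.6 and 3.7 at q = 30%, ratios of 1.6 and 1.5. With q equal in both arms, losses are roughly proportional to events.

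**6. Do other analyses restore the events?** No. SAP 6.12.8 censors at, or 1 to 90 days after, stopping study medication. The component analyses in 6.12.7 reuse the same component-specific dates. Only total mortality (6.14.5) follows deaths to study close.

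**The case against.** The best defence is that the last study visit means the End of Study or Early Termination Visit. Protocol 7.12.2 uses the phrase that way for its 30-day adverse event follow-up, and SAP 6.12 describes the 30-day SAE follow-up as running from study discontinuation. On that reading the window already starts at study exit. A fixed window is also a reasonable guard against selective reporting once systematic follow-up has ended, and SAP 6.2 and 6.12.6 promise addenda before unblinding that could define the term.

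Much of this stands: the rule may have been meant as an exit rule, and a tail after exit is defensible. It does not help the subject who has no exit visit. That subject's last visit is the last quarterly one, or the rule has no anchor at all.

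Several stronger readings are tempting, and the documents do not support them.

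- **That most between-visit events are discarded.** The 64 to 67% is a share of calendar time. An event followed by any attended visit precedes the last visit and counts.
- **That deaths are lost in the same way.** The 90-day window covers a nominal 84-day gap.
- **That the hazard ratio is biased.** Losses are roughly proportional between arms when non-return is equal, and nothing in the documents suggests that it differs.
- **That the trial loses its power.** At the 0.05 level actually used for testing, power stays above about 95% over the range examined.

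**Conclusion.** The concern holds in a limited form. As written, SAP 6.12.1 to 6.12.3 can exclude a known, EAC-confirmed primary event that occurred on study, for a subject who attends no later visit. This conflicts with Protocol 10.1 and with the discontinuation anchor in SAP 6.12. SAP 6.12.6 adds a further mismatch: events count up to 30 or 90 days past the last visit, while event-free subjects stop at that visit.

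The likely size is about 2 to 14 of 113 events. This rests on assumed values of 10 to 30% for non-return and 40 to 80% for the share of first events that are hospitalizations or parenteral starts. The case is one of validity, not power: the excluded events would come from the sickest subjects, censoring may be informative, and no planned analysis shows the effect. It should be fixed before unblinding, but it does not by itself put the primary result in doubt.

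**What to change.** In a SAP revision or the addendum already planned:

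1. In 6.12.1 to 6.12.3, count every EAC-confirmed hospitalization, parenteral start or death from randomization to the date the subject left the study (withdrawal, loss to follow-up, death or formal study conclusion), whenever the last visit was.
2. Run any 30- or 90-day tail from that date.
3. In 6.12.6, censor event-free subjects at the last contact at which event status was known, including phone contacts.
4. State that this replaces the cut-off in Protocol 10.3. Protocol 10 allows such changes to be documented in the SAP without an amendment.
5. Keep the present rule as a sensitivity analysis, and at the blinded data review report the pooled number of confirmed events that it would drop. That count replaces the assumptions used above.

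The cost is SAP wording and a change to the derivation program. No new visits or data are needed for events that are already reported and adjudicated.

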6.12.3 Initiation of a Parenteral (infusion or sub-cutaneous) Prostacyclin

Any initiation of a parenteral prostacyclin, directly related to worsening PAH (transient use [≤ 7 days] for non-PAH related illness allowable, that occurs from randomization to the 30 days following subject's last study visit is counted as an event for the primary outcome. The date of the event is the actual date of transition to parenteral prostacyclin. All those without a reported parenteral prostacyclin during the 30 days following their last visit are censored for parenteral prostacyclin at the 30 day time even if it is known that they received parenteral prostacyclin after the 30 day window.

6.12.4 Disease Progression

Disease progression is assessed at each study visit. In order to declare disease progression, a subject must meet the 6MWT decrement criterion and worsening of PAH symptoms. To satisfy the 6MWT criterion, subject must attend two study visits for 6MWT measurements: initial test and confirmatory test. Any disease progression that occurs from randomization to the subject's last study visit is counted as an event for the primary outcome. The date of the event is the actual date of disease progression as defined by the initial 6MWT test. All those without a reported disease progression up to their last visit are censored for disease progression at the last study visit even if it is known that disease progression occurred after the last study visit.

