Initial start-up activities and recruitment of subjects will be restricted to ensure subject safety. As such, the sample size determination calculations will not include the initial 6 months of the study to make certain of adequate powering for this study. The accrual period and follow-up period used will be 1.5 and 2.5 years, respectively. Thus, assuming a one-year rate of clinical worsening of 45% in the placebo (inhaled treprostinil alone) group, 25% in the BPS-314*d*-MR group (a 20% reduction from inhaled treprostinil therapy alone), proportional hazards over time, an accrual period of 1.5 years, a 0.01 two-sided significance level, and a total follow-up time of 2.5 years, an exponential maximum likelihood test of equality of survival curves would require 113 events and 116 subjects per treatment group to detect treatment difference at a power of 90% at a 0.01 two-sided significance level (or 97% power at a 0.05 two-sided significance level or approximately 90% power at a 0.05 two-sided significance level to detect a 13% reduction from an inhaled treprostinil rate as low as 30%). Therefore, this study will randomize approximately 240 subjects. Sample size calculations were performed using nQuery Advisor 7.0 using sample size methods for the log-rank statistic based on Lakatos & Lan (1992). Subjects who discontinue from the trial will not be replaced.

The Sponsor will continuously monitor the overall (pooled) event and drop-out rates during the course of the study. Sample size may be increased during the trial to maintain the planned power at between 80% and 90% and the intended trial duration. Only pooled blinded data will be used to increase sample size.

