2 STUDY OBJECTIVES

2.1 Primary Objective

The primary objective of this study is to compare the effect of esuberaprost (BPS-314d-MR) to placebo, each added to treprostinil, inhalation solution (Tyvaso®) on the composite endpoint of time-to-clinical-worsening (TtCW), defined as the time from randomization to the first of any of the following clinical worsening events:

- Death (all causes)
- Hospitalization due to worsening pulmonary arterial hypertension (PAH), defined as:
 - Non-elective hospitalization lasting at least 24 hours in duration caused by clinical conditions directly related to PAH and/or right heart failure and requiring intensification of treatment; or Lung or heart/lung transplantation; or Atrial septostomy
- Initiation of a parenteral (infusion or sub-cutaneous) prostacyclin directly related to worsening PAH (transient use [\leq 7 days] for non-PAH related illness allowable)
- Disease progression (all criteria below required):
 - A decrease in six minute walk distance (6MWD) of at least 15% from Baseline (defined as the average of the two 6MWTs performed on sequential days of the Baseline Visit), or being too ill to walk as a consequence of PAH progression, confirmed by six-minute walk tests (6MWT) performed at 2 consecutive visits,
 - Worsening of PAH symptoms, which must include either:
 - An increase in WHO Functional Class or
 - Worsening symptoms of right heart failure
- Unsatisfactory long-term clinical response (all criteria below required):
 - Receiving randomized treatment for at least 24 weeks
 - A decrease of at least 15% from Baseline (defined as the average of the two Baseline Visit 6MWTs) in 6MWD, or too ill to walk, directly related to PAH progression, at Week 24 and beyond; at 2 consecutive visits, and
 - Sustained WHO Functional Class III or IV symptoms for at least 24 weeks.

The Investigator will use the above criteria to provide an initial judgment of whether a suspected clinical worsening event has occurred. A blinded Event Adjudication Committee (EAC) will review all suspected clinical worsening events and make a final determination for each (see [Appendix 1](#)).

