6.12.5 Unsatisfactory long-term clinical response

Only subjects who have been on treatment for at least 24 weeks are eligible for meeting this definition. In order to declare unsatisfactory long-term clinical response, a subject must meet the 6MWT decrement criterion and show lack of sustained improvement in WHO functional class. Similar to disease progression, a subject must attend two study visits for 6MWT measurements: initial test and confirmatory test. Any unsatisfactory long-term clinical response that occurs from randomization to the subject's last study visit is counted as an event for the primary outcome. The date of the event is the actual date of unsatisfactory long-term clinical response (initial 6MWT test). All those without a reported unsatisfactory long-term clinical response up to their last visit are censored for unsatisfactory long-term clinical response at the last study visit.

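### SAP 6.12.4 and 6.12.5 do not carry the too-ill-to-walk limb of the primary endpoint into the component derivation, so derived events and dates may differ from those the EAC confirms

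*SAP*

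**What the plan says.** **Definition (SAP 2.1; same text in Protocol 2.1 and 7.10.1).** Two of the five components use the walk test.

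- *Disease progression* needs a fall of at least 15% from baseline "or being too ill to walk as a consequence of PAH progression, confirmed by six-minute walk tests (6MWT) performed at 2 consecutive visits", plus worse PAH symptoms.
- *Unsatisfactory long-term clinical response* needs 24 weeks of randomized treatment, a 15% fall or being too ill to walk at two consecutive visits from Week 24 on, and sustained class III or IV. Nothing in this component asks for a walk test to be performed.

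**Derivation (SAP 6.12).** The section opens by referring to 2.1 and leaves the final determination to the blinded EAC. It also says that it sets out how the time to each component is calculated.

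- SAP 6.12.4 asks for a decrement in the walk test and adds: "To satisfy the 6MWT criterion, subject must attend two study visits for 6MWT measurements: initial test and confirmatory test". The event is dated by the initial test. Without an event, the subject is censored for this component at the last study visit.
- SAP 6.12.5 likewise asks for a decrement and says that "a subject must attend two study visits for 6MWT measurements: initial test and confirmatory test". The dating and censoring rules are the same.

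Neither subsection mentions being too ill to walk.

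**Use of the dates.** SAP 5.1.1 measures time to clinical worsening (TtCW) to the first EAC-confirmed event. SAP 6.12.6 builds it from the earliest of the component dates. For time to clinical failure (TtCF), SAP 2.2 keeps too ill to walk as an alternative to the walk-distance criterion.

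**The concern.** The definition has two limbs and the derivation has one. A subject who cannot walk produces no distance, no decrement and no test from which to take a date. A programmer who codes from 6.12.4 and 6.12.5 would therefore find no event in that component for a subject who meets the clinical idea in 2.1.

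At stake is whether the analysed primary endpoint is the one that was defined and adjudicated. If the EAC works from 2.1 and the programming from 6.12, the two can disagree on whether an event occurred and on its date. The affected subjects are those whose disease has progressed most on this measure.

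**Working it through.** **1. The plan's own event figure.** Inputs from SAP 4.1: one-year worsening of 45% on placebo and 25% on active, 90% power, "0.01 two-sided significance level".

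- HR = ln(0.75)/ln(0.55) = 0.481.
- Schoenfeld events = 4 × (2.576 + 1.282)² / (ln 0.481)² = 59.5 / 0.535 = 111.2, so 112, against 113 stated.
- With 113 events, power is 90.5% at 0.01 and 97.3% at 0.05, which agrees with the stated 90% and 97%.

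The sample size is sound and this point does not affect it.

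**2. The passages side by side.**

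| | SAP 2.1 | SAP 6.12.4 / 6.12.5 |
|---|---|---|
| Disease progression | 15% fall, or too ill to walk; then confirmation by tests *performed* at two visits | decrement; two visits for measurements; dated by initial test |
| Unsatisfactory long-term response | 15% fall, or too ill to walk, at two visits; no performed test asked for | decrement; two visits for measurements; dated by initial test |

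For long-term response the derivation is plainly narrower than the definition. For disease progression the tension already lies within 2.1, because *performed* follows a limb in which no test can be performed. Reading 6.12.4 together with 2.1 does not settle it.

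**3. Four hypothetical records, read literally.** A, B and C have baseline 350 m, so the threshold is 0.85 × 350 = 297.5 m, and move from class III to IV at Week 12. D is class IV throughout and has at least 24 weeks of treatment. All visits are attended.

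| Record | First visit | Next visit | Under 2.1 | Under 6.12.4 / 6.12.5 |
|---|---|---|---|---|
| A | Week 12: 280 m (280/350 − 1 = −20%) | Week 24: too ill to walk | progression, if a visit without a walk can confirm | no confirmatory measurement, no event |
| B | Week 12: too ill | Week 24: too ill | progression, subject to *performed* | no measurement, no event, no date |
| C | Week 12: 280 m | Week 24: 275 m (275/350 − 1 = −21.4%) | progression | event dated Week 12 |
| D | Week 24: too ill | next quarterly visit: too ill | long-term response met | no measurement, no event, no date |

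C is no sicker than A or B on this measure, yet of the three only C has a derived event.

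**4. Where it would show.** It would show in TtCW, if built from component dates under 6.12.6. It would show in the component incidence analyses of 6.12.7, which use component-specific dates even when another component captures the subject. It would show in TtCF through its clinical-worsening limb, although TtCF's second limb accepts too ill to walk after 24 weeks.

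**5. Size.** The documents give no component mix and no count of too-ill visits. Suppose shares f_P and f_E of events are missed on placebo and active. To a first approximation, observed HR = HR × (1 − f_E)/(1 − f_P).

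- Equal shares leave the HR unchanged.
- Assumed f_P = 10%, f_E = 5%: 0.481 × 0.95/0.90 = 0.508.
- Assumed f_P = 5%, f_E = 10%: 0.481 × 0.90/0.95 = 0.456.

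The documents do not say which applies.

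**The case against.** The best defence is that 6.12 does not stand alone. It takes its definition from 2.1, where too ill to walk is an explicit alternative. The subsections ask the subject to attend, and a subject can attend and be recorded as too ill to walk. The endpoint is adjudicated: the EAC decides each case by consensus, and 5.1.1 uses the EAC-confirmed date. A confirmed event is dated back to the initial test, so confirmation alone adds no delay. Death stays open to 90 days after the last visit, and PAH hospitalization and parenteral prostacyclin to 30 days (SAP 6.12.1 to 6.12.3). The EAC charter excerpt in SAP Appendix 2 is not readable in the public text. The addenda promised in 6.2 (data conventions) and 6.12.6 (missing data) are not part of it. Any of these may already cover the case.

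Much of this stands. A reader might infer that the too-ill limb can never be met, or that the sickest subjects drop out of the primary analysis. The documents do not support either reading, for the reasons just given.

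What remains is narrower. By its own account, 6.12 fixes how component times are calculated, and what it fixes is a decrement, measurements and a test date. EAC confirmation says that an event occurred, but 6.12.4 and 6.12.5 offer no date for a subject with no test. Nor can 6.12.5 be assumed to copy 2.1 faithfully: it also replaces sustained class III or IV with lack of sustained improvement in class. The addendum in 6.12.6 is described as covering missing data, whereas too ill to walk is a defined outcome.

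**Conclusion.** The point holds as a conflict between the definition of the primary endpoint and its derivation. It is clear for unsatisfactory long-term response. For disease progression, 2.1 is itself ambiguous. The consequence is limited to subjects who are too ill to walk because of PAH at one or both qualifying visits. In that component they have no derived event and are censored, or they enter the primary outcome only through a later event in another component.

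Two further inferences are tempting and are not supported.

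- *That the hazard ratio is pulled toward 1.* More such subjects on placebo is not enough. A larger fraction of events would have to be missed on placebo than on active drug, and the documents do not show that.
- *That power falls.* If 10% of the 113 events were missed and not replaced, 101.7 would remain and power at 0.05 would be 95.8% instead of 97.3%. But the trial runs until 113 events (Protocol 4.3, SAP 3.1), and SAP 4.2 allows the sample size to rise to keep that target. An equal loss would mainly lengthen the trial.

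The conclusion rests on a literal reading of 6.12.4 and 6.12.5, and on the charter and addenda not already resolving it. It should be settled before unblinding.

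**What to change.** Add to SAP 6.12.4 and 6.12.5, directly or by addendum before unblinding, wording such as: *An attended visit at which no 6MWT was done because PAH left the subject too ill to walk, as confirmed by the EAC, counts as a qualifying result, initial or confirmatory. The event is dated at the first of the two consecutive qualifying visits.*

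Also:

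- State how a missed confirmatory visit is classified and dated. The wording above covers attended visits only.
- In 2.1, replace the requirement for *performed* tests with wording that admits a visit without a walk because of PAH, and bring the EAC charter into line.
- Reconcile the functional-class criterion in 6.12.5 with 2.1 at the same time.

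The cost is mostly drafting, but it reaches beyond the SAP: the same definition stands in the protocol, and events are adjudicated under the charter. It needs the record of why a walk was not done. The small downside is that attribution to PAH rests on the opinion of the investigator and the EAC, as the definition already does.
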